5.4. Demographic and Clinical Characteristics and Control Variables

Demographic and lifestyle characteristics including age, race, ethnicity, relationship status, rural/urban residence, education, income, sleep, mental health history, and physical activity will be assessed as possible confounds. The 4-item Godin Leisure Time Physical Activity survey⁴⁹ the Women's Health Initiative Personal Habits Questionnaire⁵⁰ will be used to assess physical activity, and the Pittsburgh Sleep Quality Index (PSQI) will be used to assess sleep quality.⁵¹ We will monitor (self-report) for use of psychotherapy, psychotropic medications (e.g. antidepressants, anti-anxiety medications), and service utilization (e.g., support groups) at each assessment point and control for these if necessary. Rural residence will be categorized by the US Department of Agriculture's Rural Urban Continuum Codes (RUCC) which distinguish counties by degree of urbanization and adjacency to metropolitan areas.⁵² Codes 4-9 have often been used to indicate rurality (non-metro),⁵³ whereas 7-9 have been used to indicate more isolated rural locations.

Data regarding stage, grade, pathology, recurrence, treatment, and medications will be abstracted from medical records. Subjects who come through non-clinic referrals will be asked to provide contact information for their physician and sign a release of information form as part of the consent process to verify self-reported clinical information. We will request the pathology report, most recent clinic notes, and patient insurance status.

6. Study Procedures

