6.2 Randomization

Assignment to either ML or HL will be done by cluster-randomization stratified by time slot as follows. When subjects enroll, they will provide their availability for each of 3 time slots during which a group will be offered. Subjects will be assigned to a time slot for a web group cohort according to their availability, in the order of enrollment, with each cohort comprised of 5-8 subjects. Before randomization subjects will be re-contacted to confirm that they are still available. Once a time-slot cohort of 5-8 is filled, the cohort will be randomized to either ML or HL, drawn from the corresponding stratum. The cluster-randomization for each strata will employ permuted blocks of block size 2 or 4. To avoid a cluster having a majority of participants with recurrence an exception will be made for subjects with recurrence, such that if there are already 3 subjects with recurrence in the same web-group cohort, the subject will be assigned to the next cohort at that time slot. To minimize waiting time, when the first person recruited has been waiting 3 months of longer, the cohort may begin with at least 5 subjects. Randomization lists will be generated by the statistician prior to the enrollment of subjects and allocation will remain concealed until a group of 5-8 needs to be assigned. The randomization sequence will be stored in a password protected file via a password protection software interface. The Research Coordinator will be the only person with access to this file. When a group is complete and ready to start, to facilitate planning, the group will be randomized by the research coordinator accessing the file. Upon entering an ID code for that particular group an assignment will be shown for that group. Facilitators will be informed approximately 1-2 weeks in advance so that they can plan for the group. It should be noted that facilitators' knowledge of group assignment the week before the group starts will not bias subject recruitment because the slots will have already been filled for that group. Subjects

will learn their randomization via a letter sent through mail/email. Randomization should render equal representation of racial/ethnic, SES, and geographic backgrounds, and recurrence status but we will control for any baseline differences.

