6.4 Interventions

Mindful Living Condition. This is a behavioral web-conferenced group intervention teaching stress reduction, cognitive behavioral therapy (CBT), mindfulness strategies, acceptance and commitment strategies, communication, and other skills during an introductory session and 10 1.5-2 hour sessions facilitated by a clinical psychologist and a graduate student or postdoc.

Table 4.	Weekly	Mindful	Living S	ession	Topics	and	Relaxat	ion/Me	ditation	Exercise	es
----------	--------	---------	----------	--------	--------	-----	---------	--------	----------	----------	----

Wk	Session Topic	Exercises	Linkage to sample OC issues/ concerns
1	Stress response and stress management. Developing an awareness of personal stressors. Finding meaning and sources of personal strength	Progressive muscle relaxation (PMR) & breathing	High levels of stress, and uncertainty Disease/treatment related concerns (e.g., progression, symptom burden)
2	Cognitive Appraisal: Relationships between thoughts, emotions, and physical responses.	Passive PMR with guided imagery	Fear of recurrence/death, bodily changes, dreading the worst with any new symptoms
3	Cognitive Restructuring: Demonstration & discussion on alternative responses to negative self-talk.	Autogenic relaxation	Fear of recurrence, self-image; adjusting expectations; dealing with symptoms
4	ACT: Identification of avoidance and control strategies; finding effective alternatives through personal values, acceptance, and gratitude; using defusion to reduce emotional reactivity; overcoming avoidance	Introduction to Mindfulness, Guided mindful body scan	Fear of recurrence, living in the face of uncertainty in the future, abilities, work, meaning, creating a new normal, avoiding pain and anxiety
5	Coping strategies: problem-focused or emotion- focused coping strategies. Acceptance-based strategies for painful emotions; decreasing avoidance.	Mindfulness meditation	Coping with symptoms, coping with loss of abilities, work challenges, challenges of asking for help, self-nurturance
6	Social support: Benefits & types of support. Strategies for enhancing support and meaningful relationships.	Mindfulness meditation	Changes in relationships, loss of intimacy, avoiding conversations about symptoms, death,

7	Effective communication: Becoming aware of needs and communicating them effectively.	Mindfulness meditation	Expressing needs adaptively & asking for help; doctor-patient and intimate relationships

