Subjects will be informed that they may withdraw from the study at any time, with no penalty, should this occur; conversely, we will attempt to resolve any problems causing these responses, should survivors wish to continue participating. If a participant experiences an adverse or unanticipated event during the study, research staff in contact with that participant will notify the lead investigator at each participating site or at UI if the participant is not being followed at one of the participating clinical sites. Subjects will be asked to report any new health problems that arise in connection with the study to the study coordinator at their site or to the Coordinating and Data Core at the UI if they are not from a participating clinical site. He/she will refer the survivor to their physician for serious health problems. Should a survivor disclose high levels of emotional distress (e.g. levels of depression consistent with a diagnosis of depression [CESD > 24]) during the study period, designated study personnel will contact the participant to offer appropriate resources as determined by the lead investigators. Documentation of appropriate resources offered to the survivor and of the survivor's acceptance or rejection of the resources will be made by the Coordinating and Data Core.

Study data will be collected and managed using REDCap (Research Electronic Data Capture) electronic data capture tools supported by the Biomedical Informatics group in the UI Institute for Clinical and Translational Science. REDCap (www.project-redcap.org) is a secure, web-based application with controlled access designed to support data capture for research studies, providing: 1) an intuitive interface for validated data entry; 2) audit trails for tracking data manipulation and export procedures; 3) automated export procedures for seamless downloads to common statistical packages; and 4) procedures for importing data from external sources. For multi-center studies REDCap uses Data Access Groups (DAGs) to ensure that personnel at each institution are blinded to the data from other institutions Each study team member will be granted access to REDCap through a secure login by the study PI, study manager or their proxy. REDCap supports Two-factor authentication using DUO.

Risks of Immune Marker Sub-Study:

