Descriptive statistics will be computed for all demographic and baseline variables for each of the treatment arms and distributions of continuous variables will be evaluated for normality. If data are non-normal, appropriate transformation will be applied or non-parametric methods may be used. Demographic and baseline variables will be compared between treatment groups using ttest for continuous variables, Wilcoxon-rank sum test for ordinal, and non-normally distributed continuous variables, and Pearson Chi-square test for categorical variables. Variables found to differ significantly between the groups will be used as covariates in the comparison of outcome measures between the treatment groups. A number of variables known to influence our primary outcomes (e.g., income, education, marital status, and race/ethnicity) will be considered as possible covariates. These putative control measures will be analyzed as covariates if they are correlated with our outcomes (at p<.10). The internal consistency (coefficient alpha) and testretest correlations over the course of data collection will be evaluated for multi-item inventories. While every effort will be made to follow-up with subjects, it is expected that approximately 25% of the subjects may be lost across the study period. Intent to Treat (ITT) analysis will be performed using all available data for all randomized subjects. Reasons for subject drop-out will be recorded and compared between treatment groups. Subject characteristics and outcome measures collected prior to drop-out will be compared to those that complete the study follow-up. In the presence of missing data, under the assumption of missing at random (MAR), linear mixed model analysis, which can handle incompletely observed subjects and uses a likelihood estimation method, will provide correct likelihoods and lead to valid estimates. However, since the data under analysis cannot distinguish if data is MAR or if it is missing not at random (MNAR), sensitivity analysis will also be performed using pattern mixture models. Multiple imputation will be used for sensitivity analysis by imputing from a non-random pattern mixture model. Per protocol analyses will be performed including participants that attended at least 6 sessions of their respective intervention condition and completed the immediate post-intervention surveys or any subsequent follow-up surveys.

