AAQ	2.8	2.5	0.284	2.3 (0.65)	2.5 (0.71)	-2.7 (-0.76)	(-6.3, 1.0)

Table 6. Power Considerations

7.1. Statistical analyses for Aim 1

Aim 1 will be tested using linear mixed model (LMM) analyses for repeated measures with treatment group (ML vs. HL), time, and treatment*time interaction as fixed effects. Random effects include web group cohort (within treatment) and subjects (within cohort, within treatment). In fitting the LMM, appropriate covariance structures for the longitudinal measures within subject will be considered, such as compound symmetry, or heterogeneous compound symmetry, and then selected based on Akaike Information Criteria (AIC) and Schwarz's Bayesian Information Criteria (BIC). Specifically, to test for immediate change (post-intervention), the linear mixed model analysis will include the baseline and immediate post-intervention timepoints. The difference in immediate change post-treatment between the different conditions will be tested by the interaction effect. For the mixed model analysis of long-term change, data from all 4 timepoints will be used in fitting the model, with the difference in long-term change at 6 and 12 months assessed using tests of mean contrast. Bonferroni adjustment will be applied to the p-value to test for long-term change at 6 and 12 months. For each of the two analyses, if confounding variables are found to differ between the treatment groups such that covariate adjustment is necessary, a secondary comparison of the primary outcome variable between treatment groups will be made by expanding the LMM to include covariates. These variables may include age, education, income, race/ethnicity, geographic location, recurrence, maintenance chemotherapy, recurrence during the study period, and disease stage. Statistical significance for efficacy of ML vs. HL will be based on a two-tailed test at the 0.05 significance level with treatment effect summarized as mean difference with 95% confidence interval. Similar analyses will be performed for the secondary outcome measures.

7.2. Statistical analyses for Aim 2

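### Sections 7 and 6.2 disagree with 7.1 on covariates in the Aim 1 comparison, 5.4 and 7.1 permit adjustment for post-randomisation variables, and the time-slot stratum is in no model

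*Combined protocol and SAP*

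**What the plan says.** Four places bear on which covariates enter the Aim 1 comparison.

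- **Section 7 (Statistical Evaluation/Considerations)** gives two selection rules. After baseline testing by t-test, Wilcoxon or chi-square, "Variables found to differ significantly between the groups will be used as covariates in the comparison of outcome measures between the treatment groups". For income, education, marital status, race/ethnicity and similar variables, "These putative control measures will be analyzed as covariates if they are correlated with our outcomes (at p<.10"). Neither rule is limited to a secondary analysis.
- **6.2 Randomization** says that randomisation should balance the arms, "but we will control for any baseline differences". No threshold is given.
- **7.1** defines the Aim 1 mixed model with treatment, time and treatment-by-time as fixed effects, and cohort and subject as random effects. If confounders differ between arms, "a secondary comparison of the primary outcome variable between treatment groups will be made by expanding the LMM to include covariates". The candidate list ends with "maintenance chemotherapy, recurrence during the study period, and disease stage".
- **5.4** says the study will monitor psychotherapy, psychotropic medication "and service utilization (e.g., support groups) at each assessment point and control for these if necessary". It gives no criterion and does not say which model.

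6.2 Randomization stratifies the cluster randomisation by three time slots. Time slot appears neither in the 7.1 model or covariate list, nor in the Aim 2 plan (7.2), nor in the Aim 3 model (7.3).

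**The concern.** There are three separate issues.

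**(a) Which model governs.** The sections give four triggers for adjustment: a significant baseline difference, correlation with outcome at p<.10, any baseline difference, and confounders that differ. They also give two roles for the adjusted model. The efficacy sentence in 7.1 does not say whether it refers to the unadjusted or the adjusted result.

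**(b) Post-randomisation covariates.** On-study recurrence and service use at follow-up are measured after allocation. The plan is an intention-to-treat comparison. Adjusting for a variable that the assigned arm changes removes or adds part of the effect being estimated; if the arm does not change it, there is no such bias. The protocol suggests two ways in which use could differ by arm. Under 6.5, when a woman discloses high distress, "designated study personnel will contact the participant to offer appropriate resources as determined by the lead investigators"; later use can therefore follow CES-D, a primary outcome. And Mindful Living session 6 (6.4, Table 4) covers "Strategies for enhancing support and meaningful relationships", while support groups are among the 5.4 variables.

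**(c) The stratum.** An analysis should normally reflect the factor used to restrict randomisation. Because Aim 1 tests change from baseline, slot-by-time is the term that bears on the contrast.

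**Working it through.** **Reproducing the plan's figures.** Inputs from Section 7 and Table 6: two-sided 0.05, 80% power, 16 cohorts per arm, 6 analysed per cohort (96 per arm), residual SD and ICC by outcome. Detectable immediate difference = 2.80 × √2 × residual SD × √(2/96) × √(1 + 5 × ICC):

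| Outcome | Residual SD | ICC | Result | Table 6 |
|---|---|---|---|---|
| FACT-Total | 9.3 | 0.010 | 5.45 | 5.5 |
| PSS | 4.2 | 0.010 | 2.46 | 2.5 |
| CES-D | 5.3 | 0.150 | 4.01 | 4.1 |

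The table therefore applies the ICC to change, and the power model has no covariates and no slot term.

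**(a) Baseline covariates.**
- *How often it arises.* 7.1 names eight baseline variables. If they are independent and each is tested at 0.05, the chance of at least one false flag is 1 − 0.95^8 = 0.34.
- *Effect on the estimate.* A time-constant covariate entered as a main effect nearly cancels from treatment-by-time. Simulation: 300 data sets per setting, 32 cohorts of 8, CES-D SDs from Table 6, cohort SD 3.0 assumed, covariate correlation with usual CES-D 0.3 or 0.5 assumed. The shift is 0.000 with complete data. With 26% dropout the mean absolute shift is 0.042 or 0.067 points (95th percentile 0.105 or 0.160), against a standard error of 1.065.
- *Type I error.* In cohort-level simulations (assumed covariate R² 0.2 to 0.4), either rule alone gave 0.041 to 0.055. Reporting whichever model had the smaller p gave 0.052 to 0.069.

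**(b) Post-randomisation covariates.** Approximate shift = change in use caused by Mindful Living × CES-D gap between users and non-users. Both inputs are assumed.
- Low end: 0.05 × 3 = 0.15 points; 0.15/4.1 = 4% of the detectable difference.
- High end: 0.15 × 9 = 1.35 points; 1.35/4.1 = 33%.
- Direction: toward the null if Mindful Living lowers use, away if it raises use, zero if it does not change use.
- Distress-referral route in 6.5 only, assuming HL mean CES-D 10 to 18, uptake 30% to 70%, background use 10% and a 4.1-point effect: use differs by 1 to 6 percentage points, but the shift is 0.00 to 0.14 points in the immediate model and 0.01 or less with four timepoints.

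**(c) Time slot.** Let f be the share of cohort clustering of change that slot explains (assumed), with 6 per cohort and slots balanced by arm.

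*If clustering of change is modelled* (for example, a cohort-level analysis), the standard error with slot-by-time relative to without it is √[(6·ICC·(1−f) + 1 − ICC)/(1 + 5·ICC)]:
- ICC 0.010: √(1.02/1.05) = 0.986 for f = 0.5; √(0.99/1.05) = 0.971 for f = 1.
- ICC 0.150: √(1.30/1.75) = 0.862 for f = 0.5; √(0.85/1.75) = 0.697 for f = 1.
- f = 0: no gain; the critical t moves from 2.042 (30 df) to 2.048 (28 df).

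*If 7.1 is read literally*, the random effects are cohort and subject only, with no cohort-by-time term, so the standard error of the change contrast ignores clustering of change. Per-subject variance acting on the contrast is V = 6·ICC·(1−f) + 1 − ICC. The model uses about 1 without slot-by-time and 1 − f·ICC with it. Type I error = 2·P(Z > 1.96/√(V/model variance)). For ICC 0.150:

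| f | V | Without slot-by-time | With slot-by-time |
|---|---|---|---|
| 0 | 1.75 | 1.96/√1.75 → 0.138 | 0.138 |
| 0.5 | 1.30 | 1.96/√1.30 → 0.086 | 1.96/√(1.30/0.925) → 0.098 |
| 1 | 0.85 | 1.96/√0.85 → 0.034 | 1.96/√(0.85/0.85) → 0.050 |

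Simulation of 8,000 trials per setting agrees: 0.139, 0.084 and 0.036 without; 0.141, 0.094 and 0.051 with.

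**The case against.** **On (a),** 7.1 is the specific plan for Aim 1, and Section 7 can be read as saying which variables qualify while 7.1 says in which model. The remark in 6.2 Randomization closes a procedural section. This is a fair reading, and the numerical consequence is small, but no passage says that 7.1 governs. A reader might infer that the covariate rules distort the efficacy result; the calculations do not support that unless the better of two models is picked.

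**On (b),** a reader might infer that post-randomisation adjustment is planned for the primary test. The documents do not say so. On-study recurrence appears only in the 7.1 secondary comparison, as something that may be included. The 5.4 variables are absent from the 7.1 list and reach the main test only if 5.4 is read over 7.1. Nor do the documents establish that use will differ by arm: the 6.5 offer applies to both arms, and session 6 does not mention referral to support groups or therapy. Table 3 schedules CES-D only before randomisation and at weeks 12, 26 and 52, so in the immediate model the 6.5 route needs unscheduled disclosure of distress. All of this stands. What remains is permission, without criterion or named model, to adjust for variables that allocation may affect.

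**On (c),** it is tempting to say that omitting the stratum only makes the test conservative. That holds where clustering of change is modelled. Under the random effects stated in 7.1, it fails unless slot explains most of the clustering.

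**Conclusion.** The point holds as a matter for correction before analysis, with limited demonstrated size.

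- **(a)** The passages conflict on wording and should agree; the effect on treatment-by-time is small under the assumed correlations and dropout.
- **(b)** This is the most important part. Adjusting for on-study recurrence or post-baseline use biases the total effect of assignment if Mindful Living changes them, and not otherwise. The magnitude is unknown. The range of 0.15 to 1.35 CES-D points rests wholly on assumed inputs, and the one route modelled from the protocol gives at most 0.14 points under assumed uptake. A reader should not take one third of the detectable difference as an expected bias. No figure is available for on-study recurrence.
- **(c)** Time slot is omitted throughout. With clustering of change modelled, this costs at most 3% of the standard error for FACT-O and PSS and up to 30% for CES-D, the latter only if slot explained all clustering, which nothing in the documents suggests. Under 7.1 as written, the larger risk to type I error for CES-D is the unstated cohort-by-time effect, and slot-by-time alone does not restore 0.05.

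**What to change.** 1. State in Sections 7 and 6.2 Randomization that the 7.1 model is the primary Aim 1 test. Delete covariate selection by baseline significance tests and by the p<.10 rule. Make any adjusted model secondary, using baseline covariates named in advance and recorded before allocation. The last condition matters because Table 3 note d allows pre-group assessments after randomisation, and 6.3 has some rescheduled women repeat baseline surveys.
2. Remove on-study recurrence (7.1) and post-baseline psychotherapy, psychotropic drug and service use (5.4) from all efficacy models. Report them by arm and use them only in analyses labelled exploratory.
3. Add time slot and slot-by-time as fixed effects, using the slot in which the woman's cohort was randomised, together with a cohort-by-time random effect or an equivalent cohort-level analysis of change.

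The cost is SAP wording, a flag for whether each baseline assessment preceded allocation (assumed derivable from survey and randomisation dates), and a few degrees of freedom: slot-by-time uses (3−1)×(2−1) = 2 in the immediate model and (3−1)×(4−1) = 6 with four timepoints. No new data collection is needed.

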Aim 1 tests whether the Mindful Living vs. HL intervention increases HRQOL, and decreases in perceived stress (primary), and decreases anxiety, depressive mood, and fatigue (secondary) during a 11-week intervention, and whether changes are sustained over a 12-month follow-up. Based on preliminary data, there will be a detectable differences in mean immediate (post-treatment) change from baseline and in mean sustained change (6 and 12 month) from baseline, for the primary and secondary outcome measures between the ML and the HL arms with an anticipated final sample size of 192 subjects. The detectable group mean difference was calculated for a two-tailed test at the 0.05 significance level with 0.80 power for a final sample

size of 96 subjects per treatment arm for a cluster-randomized design with corresponding intracluster correlation coefficient (ICC) estimated from our pilot data. The 96 subjects are from 16 web-groups (cohorts) per arm with an average of 6 subjects per cohort. This assumes 25% dropout, so that a total of 256 subjects will be enrolled, comprised of 32 cohorts, with 8 subjects per cohort, that will be randomized to one of the two treatment arms. Based on the calculations below we anticipate that our sample size and the variability in our data will enable us to detect smaller intervention effects than those observed in our pilot for our primary variables and for several of our secondary variables for Aims 1 and 2. The effect sizes we anticipate being able to detect are consistent with the medium effect sizes generally observed in other studies of psychosocial interventions in cancer survivors.

	SD		Detectable difference (effect size=diff/pooled SD)			Between Group Difference in Immediate Change (from pilot)	
Outcome Variables Aim 1	Between Subject	Residual	ICC	Immediate (Post-tx)	Sustained (6 and 12 mo.)	Observed Mean (effect size)	95% CI
FACT-Total	13.6	9.3	0.010	5.5 (0.19)	6.1 (0.46)	9.1 (0.69)	(-3.7, 22.0)
PSS	7.1	4.2	0.010	2.5 (0.29)	2.8 (0.47)	-6.7 (-1.13)	(-12.6, - 0.9)
CESD	7.6	5.3	0.150	4.1 (0.34)	4.5 (0.60)	-5.8 (-0.77)	(-13.0, 1.5)
POMS-anxiety	4.1	2.9	0.078	2.0 (0.49)	2.2 (0.54)	-2.0 (-0.49)	(-6.0, 1.9)
POMS-fatigue	4.6	2.9	0.204	2.4 (0.59)	2.7 (0.66)	-2.0 (-0.49)	(-5.9, 1.9)
AIM 2							
MOCS relaxation	1.4	1.2	0.125	0.9 (0.53)	1.0 (0.59)	3.0 (1.77)	(1.0, 5.0)
MOCS coping	4.1	1.8	0.010	1.1 (0.43)	1.2 (0.47)	3.8 (1.49)	(0.7, 6.9)
FMI	7.4	3.5	0.010	2.1 (0.42)	2.3 (0.46)	3.5 (0.71)	(-1.7, 8.8)

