The statistical analyses for Aim 2 will examine potential mediators of any observed intervention effects on outcome measures, with examination of skills that support post-intervention and sustained skills. For Hypothesis 2A effects of the intervention on relaxation, coping, mindfulness and acceptance outcomes, the analytic plan will be similar to those in Aim 1, with similar targeted effect sizes and similar power projections. For Hypothesis 2b, testing mediation of intervention effects, mediation analysis will explore the causal pathway between intervention (ML and HL) and changes in primary outcomes (HRQOL, depressed mood, and perceived stress) and secondary outcomes (anxiety and fatigue) from baseline to post-intervention (immediate) and from baseline to 12 months (sustained) with change in reported relaxation, mindfulness, acceptance, and cognitive coping skills as mediators. With the independent variable X (intervention) randomized to web-group cohorts, and the mediator variables M (change in mastery in relaxation, mindfulness, avoidance, and cognitive coping skills), and the dependent variable Y (change in HRQOL, depressive mood, stress, and secondary variables) measured at the subject level within cohorts, we have a two-level hierarchy with a 2-1-1 design. For this multilevel design, multilevel structural equation modeling (MSEM) will be used to estimate and test the direct and indirect effects to assess multilevel mediation⁵⁷ using SEM or GSEM in Stata or MPLUS.

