Power for Hypothesis 2B is based on the pilot data where large effects of group assignment (ML vs. HL) were observed on changes in potential mediators (relaxation, coping skills, mindfulness, and acceptance; range of d = .70-1.7). In the proposed model multilevel mediation framework this effect will include some variance attributable to the cohort to which the subject is randomized within the treatment arm, as well as the effect of the treatment itself, the latter of which is the effect of interest. We therefore conservatively estimate the true treatment effect for the mediators to be d = .60, representing the first arm of the mediation pathway. The second arm of the mediation pathway reflects the association between change in the mediators (relaxation, coping, mindfulness, and acceptance) and change in the outcomes of interest (HRQOL, stress, etc.) In our pilot work shown above, the absolute correlation values between these change variables ranged from .41-.76, corresponding to a d range of .89-2.3,58 and we conservatively adopt this lower estimate (.89) for purposes of estimating power. Here we use the Monte Carlo approach for evaluating indirect (mediation) effects with 5000 replications and two Monte Carlo draws per repetition and an attrition-adjusted sample size of 192 (96 per group).⁵⁹ This produces power in excess of .99 for calculating significant mediated effects with a 95% confidence interval. In the event that the true effect sizes are substantially smaller (i.e., d=0.4 rather than .6 for the first path, and d = .6 rather than .89 for the second path) we will still have .80 power to detect significant mediated (indirect) effects.

7.3. Statistical Analyses for Aim 3

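### Section 7.1's model leaves between-cohort variance in change out of the treatment-by-time test, although Table 6 counts it; CES-D false-positive error is then about 5% to 14%

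*Combined protocol and SAP*

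**What the plan says.** Section 7.1 specifies a linear mixed model with treatment, time and their interaction as fixed effects. On the random part it says: "Random effects include web group cohort (within treatment) and subjects (within cohort, within treatment"). What is left open is the subject-level structure: "appropriate covariance structures for the longitudinal measures within subject will be considered", with compound symmetry and its heterogeneous form as examples. For the immediate effect, "The difference in immediate change post-treatment between the different conditions will be tested by the interaction effect". The 6- and 12-month effects are contrasts from a four-timepoint model, with Bonferroni adjustment.

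The power paragraph in section 7 says the detectable differences, which are in mean change from baseline, were "calculated for a two-tailed test at the 0.05 significance level with 0.80 power", for a "cluster-randomized design with corresponding intracluster correlation coefficient (ICC) estimated from our pilot data". It assumes 96 analysed per arm in 16 cohorts averaging six. It does not say whether the ICC refers to scores at one time or to change.

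Section 7.2 analyses Hypothesis 2a in a manner similar to Aim 1. For Hypothesis 2b it treats change scores as nested in cohorts. On the effect of assignment on change in the mediators it says "this effect will include some variance attributable to the cohort to which the subject is randomized within the treatment arm".

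The status of CES-D varies. Hypothesis 1 in section 3, section 5.1 and section 7.2 ("changes in primary outcomes (HRQOL, depressed mood, and perceived stress") make it primary. The Aim 1 paragraph of section 7 lists "decreases anxiety, depressive mood, and fatigue (secondary").

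**The concern.** Whole web groups are randomised, and their members then share facilitators and discussion for 11 weeks. If members of a group tend to change together, the standard error of the arm difference in change must include that shared component. In the listed model it does not. A cohort intercept takes the same value at baseline and follow-up and subtracts out of change, exactly with complete data and approximately with dropout. Neither within-subject structure named in section 7.1 puts cohort-level variance in change back.

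The result would be standard errors that are too small and p-values below 0.05 more often than the stated level allows. The outcomes with sizeable ICCs in Table 6 are the exposed ones: CES-D, POMS-anxiety, POMS-fatigue, MOCS relaxation and AAQ. Whether a primary outcome is among them depends on the unresolved status of CES-D.

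**Working it through.** **Inputs (section 7 and Table 6).** Two-sided alpha 0.05, power 0.80, 96 analysed per arm, 16 cohorts per arm, mean of six per cohort. Residual SD and ICC by outcome; for CES-D, 5.3 and 0.150.

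**Step 1: reproduce Table 6.** SD of change = sqrt(2) x residual SD. Design effect DE = 1 + (6 - 1) x ICC. Detectable difference = (critical value + power quantile) x SD of change x sqrt(2/96) x sqrt(DE).

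For CES-D, the SD of change is 1.414 x 5.3 = 7.50 and DE = 1 + 5 x 0.150 = 1.75. The standard error is 7.50 x sqrt(2/96) = 1.08 without DE and 1.08 x sqrt(1.75) = 1.43 with it. The normal version gives (1.96 + 0.84) x 1.43 = 4.01.

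| Outcome | ICC | With DE (normal to t, 30 df) | Stated | Without DE (normal) |
|---|---|---|---|---|
| FACT | 0.010 | 5.45–5.63 | 5.5 | 5.32 |
| PSS | 0.010 | 2.46–2.54 | 2.5 | 2.40 |
| CES-D | 0.150 | 4.01–4.14 | 4.1 | 3.03 |
| POMS-anxiety | 0.078 | 1.96–2.02 | 2.0 | 1.66 |
| POMS-fatigue | 0.204 | 2.36–2.44 | 2.4 | 1.66 |
| MOCS relaxation | 0.125 | 0.87–0.90 | 0.9 | 0.69 |
| MOCS coping | 0.010 | 1.05–1.09 | 1.1 | 1.03 |
| FMI | 0.010 | 2.05–2.12 | 2.1 | 2.00 |
| AAQ | 0.284 | 2.22–2.30 | 2.3 | 1.43 |

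The rows with ICC 0.010 hardly discriminate. The five rows with larger ICCs do, and they fit only with DE. Applying DE to the SD of scores instead, sqrt(7.6² + 5.3²), gives 4.96 for CES-D, which does not fit either. Table 6 therefore counts between-cohort variance in change.

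**Step 2: true error of the listed test.** The standard error omits the factor sqrt(DE), so true size = 2 x (1 - Phi(1.96/sqrt(DE))), with DE computed from the part of the ICC that lies in change.

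| Outcome | None in change | Half | All |
|---|---|---|---|
| CES-D | 5.0% | 9.5% | 13.8% |
| POMS-anxiety | 5.0% | 7.3% | 9.6% |
| POMS-fatigue | 5.0% | 11.1% | 16.8% |
| MOCS relaxation | 5.0% | 8.7% | 12.4% |
| AAQ | 5.0% | 13.4% | 20.8% |
| FACT, PSS | 5.0% | 5.3% | 5.6% |

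For CES-D with all of the ICC in change, 1.96/sqrt(1.75) = 1.48, which gives 13.8%. Each long-term test at 0.025 becomes 9.0%.

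**Step 3: simulation.** The complete-data change test, to which the listed model reduces, rejected a true null in 5.0%, 9.5% and 13.8% of simulated trials at a change ICC of 0, 0.075 and 0.15. REML fits of the listed model used the CES-D SDs, eight enrolled per cohort and 25% random dropout. They rejected in 15.1% of 1,247 trials (Monte Carlo SE 1.0 points) with all of the ICC in change, in 9.7% of 557 (SE 1.3) with half in change and half in level, and in 4.9% of 1,201 (SE 0.6) with level only.

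**Step 4: can the pilot settle which ICC it is?** Pilot CI half-width divided by the SD of change is 0.95 to 0.98 for the five Aim 1 outcomes and does not rise with the ICC. For Aim 2 it is 1.18 (relaxation), 1.22 (coping), 1.06 (FMI) and 1.03 (AAQ); the largest belongs to an outcome with ICC 0.010. An ICC of level cannot be excluded.

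**The case against.** The strongest reply is that the harm is conditional. No text says the pilot ICC is of change, and the pilot intervals show no sign of clustering in change. If cohorts differ only in level, the listed test holds its size and Table 6 is merely conservative. This stands, and it is why the error is given as a range.

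Second, the sentence on random effects is not strictly a closed list, so an analyst could add a term. That is true, but an analyst following the text would omit it, and adding it after seeing the data would leave a borderline result open to challenge.

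Third, the section 7.2 remark about cohort variance concerns mediators and is there to justify a smaller assumed effect; it says nothing directly about CES-D. That is fair. It is supporting evidence only, and the main evidence is Table 6.

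Fourth, 14% is not a bound. It belongs to six analysed per cohort. At a change ICC of 0.15, eight per cohort gives 17.1%. Section 6.2 allows cohorts of five to eight; at 75% retention, five enrolled (3.75 analysed) gives about 10% and 6.5 enrolled (4.875 analysed) about 12%. This also stands.

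Finally, FACT-O and PSS, which every section treats as primary, are barely affected at their stated ICC.

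**Conclusion.** The concern holds and should be fixed. The cancellation of the cohort intercept is algebra, and the mismatch with Table 6 follows from the plan's own figures. The size of the harm is conditional: for CES-D, true error of about 5% if clustering is in level only, rising to about 14% if the whole ICC of 0.150 is in change, with 16 cohorts per arm and six analysed in each. For FACT-O and PSS the error is at most about 5.6% at the stated ICC. If their ICC of change were 0.05 or 0.10, an assumption outside the documents, the formula in step 2 gives 8.0% or 11.0%.

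**What to change.** 1. In section 7.1, add a random cohort-by-time effect (a cohort-specific deviation at each post-baseline visit) with Kenward-Roger or Satterthwaite degrees of freedom. State that the term stays in the model even if its variance is estimated at zero. Apply this to the two-timepoint model, the four-timepoint model and Hypothesis 2a.
2. State in Table 6 whether the ICC is of scores or of change. The arithmetic uses it as an ICC of change.
3. Reconcile the status of CES-D between Hypothesis 1, sections 5.1 and 7.2, and the Aim 1 paragraph of section 7.

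In simulation, the test with a cohort-by-time term, Satterthwaite degrees of freedom and a variance allowed to reach zero held its error at 4.0% to 5.0% for change ICCs of 0, 0.075 and 0.15.

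The cost is a sentence of SAP text and one extra random-effect line. If there is no clustering in change, intervals widen by about 3–4% at 30 df (2.042/1.973 = 1.035; 2.042/1.960 = 1.042). If the CES-D ICC is in change, they widen by about a third or more (1.43/1.08 = 1.32, before the degrees of freedom). Planned power hardly moves: at the stated immediate differences with 30 df it is 0.78 for FACT-O and 0.79 for both PSS and CES-D.
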